Rationale: The above changes were prompted by the number of suboptimally managed cases of diarrhea, one of which resulted in colitis. These changes, including the addition of adverse event assessments at Weeks 7 and 11, have been made to increase monitoring of diarrhea.

Other changes are as follows:

- Added collection of additional blood sample at 4-week Post-Surgical Follow-Up visit for ctDNA and plasma protein biomarkers analysis.

Rationale: This is aimed to enable correlation of response with biomarkers and potential identification of high-risk population(s)

- Requirement added for Target Lesion #2, if selected, to be ≥ 10 mm.

Rationale: No minimum size was previously defined; therefore, this change was made to improve clarity.

- Added additional restriction to the following exclusion criterion: “History of prior or currently active small or large intestine inflammation (such as Crohn’s disease or ulcerative colitis). *Any patient with a baseline medical condition involving the gastrointestinal (GI) tract or who may have a predisposition for GI toxicity requires prior approval from the Medical Monitor.*”

Rationale: This was added with the intention that it may further prevent patients with potential predispositions to GI side effects from being enrolled.

- Included “Investigational Agents” amongst prohibited Concomitant Therapies.

Rationale: This was not previously specified; therefore, this change was made to improve clarity.

- Added specification that there is a 4-week “wash-out” period for any other Investigational Agents prior to initiation of treatment with GDC-0032.

Rationale: This was not previously specified; therefore, this change was made to improve clarity

Additional minor changes have been made to improve clarity and consistency. Substantive new information appears in italics. This amendment represents cumulative changes to the original protocol.

PROTOCOL AMENDMENT, VERSION 4: SUMMARY OF CHANGES

GLOBAL CHANGES

Non-serious has been deleted from “non-serious adverse event of special interest” throughout the protocol.

IND number has changed from 110184 to 121658

Medical Monitor has changed from [REDACTED] to [REDACTED], M.D. Ph.D.

PROTOCOL SYNOPSIS

The protocol synopsis has been updated to reflect the changes to the protocol, where applicable.

LIST OF AUTHORS

[REDACTED], and [REDACTED] were added and [REDACTED] was removed from the list.

SECTION 1.3: BACKGROUND ON THE PI3K/AKT/MTOR PATHWAY AND BREAST CANCER

Genes in the PI3K/AKT/mTOR signaling pathway are frequently mutated or amplified in breast cancer, especially in the ER+ subtype (Cancer Genome Atlas Network [CGAN] 2012). Molecular alterations of the PI3K/AKT/mTOR pathway include the following: (1) Mutations or amplifications in *PIK3CA*, the gene encoding the alpha catalytic subunit of PI3K (p110 α) (Saal et al. 2005; Wu et al. 2005); (2) Alterations in the tumor suppressor gene *PTEN*, either by loss of protein expression (PTEN null), inactivation mutations and/or epigenetic deregulation through promoter hypermethylation (García et al. 2004); (3) PDKP1 amplification and/or overexpression (Brugge et al. 2007); (4) AKT1 somatic *gain-of-function* mutations (Stemke-Hale et al. 2008) and AKT2 amplifications (Bellacosa et al. 1995). Overall, it is estimated that up to 70% of breast cancers can have some form of molecular aberration of the PI3K/AKT/mTOR pathway (CGAN 2012).

SECTION 1.4: BACKGROUND ON REVERSING HORMONAL RESISTANCE BY INHIBITING THE PI3K/MTOR/AKT PATHWAY

In the setting of ER+ breast cancer, *the PI3K signaling pathway* seems to play an important role in mediating hormonal resistance and is a viable therapeutic target. Hyperactivation of this signaling pathway was proved to promote both *de novo* (*primary*) and acquired (*secondary*) resistance to hormone therapy in ER+ breast cancer cell lines and xenograft models (Sabnis et al. 2007), ~~and simultaneous~~ *Simultaneous* blocking of the PI3K/AKT/mTOR pathway with everolimus, *an mTOR inhibitor*, and the ER pathway with letrozole enhances antitumor activity of either agent alone (Boulay et al. 2005). Importantly, a baseline protein signature of PI3K activation was found to be predictive of a poor prognosis after adjuvant endocrine therapy (Miller et al. 2010).

In the clinical setting, impressive results of the combination of exemestane and everolimus, ~~an mTOR inhibitor,~~ were reported in the BOLERO-2 trial (Baselga et al. 2009)....

SECTION 1.5: BACKGROUND ON NEOADJUVANT THERAPY IN BREAST CANCER

...In September 2013, the Food and Drug Administration (FDA) granted accelerated approval of *pertuzumab* (Perjeta[®]) as part of a complete treatment regimen for patients with HER2-positive, locally advanced, inflammatory, or early stage breast cancer in the neoadjuvant setting.

SECTION 1.6: BACKGROUND ON GDC-0032

GDC-0032 has demonstrated activity in *preclinical* models of *PIK3CA*-mutant breast tumors in vivo as a single agent and in combination with standard of care (e.g., paclitaxel or docetaxel) or endocrine therapies (e.g., letrozole or fulvestrant)....

SECTION 3: STUDY DESIGN

In addition to the safety assessments conducted at the scheduled follow-up visits, patients will be contacted by telephone for a general assessment of adverse events at Weeks 7 and 11.

Blood samples for exploratory endpoint analysis will be collected on Day 1 prior to dosing, at Week 9, ~~and~~ prior to surgery (*Week 16 visit,*) and at the 4-weeks postsurgical follow-up visit.

SECTION 3.3.1: Rationale for Conducting the Study in the Neoadjuvant Setting

...Known as the intrinsic subtypes of breast cancer, these groups of tumors have revealed critical differences in incidence, survival, and response to treatment (*Sotiriou et al. 2003*). As genomic studies evolve, further sub-classifications of breast tumors are expected to emerge. Thus, a major challenge in breast cancer management is how to prospectively select patients who will derive the maximum benefit from a given drug regimen and minimizing unnecessary toxicities for patients with non-responsive disease.

SECTION 3.3.3: Rationale for Control Group

The *Immediate Preoperative Anastrozole, Tamoxifen, or Combined With Tamoxifen* (IMPACT) trial was a randomized, Phase II, double-blind, double-dummy, multicenter trial that randomly assigned 330 postmenopausal women with ER+ operable or locally advanced, potentially operable breast cancer in a 1:1:1 ratio to receive a daily dose of anastrozole 1 mg and tamoxifen placebo, tamoxifen 20 mg and anastrozole placebo, or a combination of tamoxifen 20 mg and anastrozole 1 mg for 12 weeks before surgery....

The American College of Surgeons Oncology Group (ACOSOG) Z1031 trial compared three AIs in a randomized, Phase II, neoadjuvant trial designed to select agents for Phase III investigations....

SECTION 3.3.4.1: Rationale for Efficacy Outcome Measure of Pathologic Complete Response

In trials of neoadjuvant hormonal therapy, pCR is an unlikely event. For instance, in the neoadjuvant trial comparing everolimus plus letrozole to letrozole *plus placebo*, pCR rates were 1.4% and 0.8%, respectively (Baselga et al. 2009).

In September of 2013, the FDA granted accelerated approval of *pertuzumab* (Perjeta®), an HER2 dimerization inhibitor, as part of a complete treatment regimen for patients with HER2-positive, locally advanced, inflammatory or early stage breast cancer in the neoadjuvant setting.

SECTION 3.3.7: Rationale for GDC-0032 Dosage

As of 5 July 2013, 34 patients have been enrolled into the dose-escalation stage of Study PMT4979g, and 56 patients have been enrolled into the single-agent expansion cohorts at 9 mg in Stage 2 (Cohorts A-D and G). All patients received GDC-0032 in capsules. Five dose-escalation cohorts (i.e., 3, 5, 8, 12, and 16 mg daily) were tested (see Section 1.7.1). The maximal administered dose was 16 mg. To obtain more safety data on long-term tolerability, the recommended single-agent dose and schedule for the single-agent GDC-0032 expansion stage ~~is~~ *was* 9-mg capsules daily.

Of the 19 efficacy-evaluable patients treated with GDC-0032 in combination with letrozole, one patient at 6 mg capsule had a cPR. The *PIK3CA* mutation status of this patient is unknown. Since efficacy has been observed at 6 mg capsules, and the long-term safety suggests that 6 mg capsule is better tolerated, the neoadjuvant study will utilize 6-mg GDC-0032 capsules in combination with letrozole.

Of the 27 efficacy-evaluable patients treated with GDC-0032 in combination with fulvestrant, 2 confirmed partial responses were observed at 6 mg capsules and 1 confirmed partial response at 9 mg capsules.

Colitis has been observed with an incidence rate of 6.2% (10/160 patients). The time (from the first dose of study treatment) to onset of colitis ranged from approximately 82–248 days as either a single agent or in combination with letrozole or fulvestrant. Most of the colitis cases have been observed at the 9-mg capsule dose level or higher. To mitigate the late-onset adverse events, such as colitis, an intermittent dosing schedule will be applied. With the 40-hour half-life, a limited impact on efficacy is anticipated....

SECTION 3.3.8: Rationale for Biomarker Assessments

Next generation sequencing (NGS) techniques, like deep genome sequencing, may offer a unique opportunity to identify such biomarkers of response. For example, using whole

genome sequencing, a two base-pair deletion in the *tuberous sclerosis 1 (TSC1)* gene was found in a patient with metastatic bladder cancer with a prolonged response (>2 years) to everolimus as single agent (Iyer et al. 2012). Among 13 additional patients with bladder cancer treated with everolimus in the same trial, those with *TSC1* mutant tumors remained on therapy longer than those with WT tumors (7.7 vs. 2.0 months, $p=0.004$), suggesting that mTORC-1 directed therapies may be most effective in patients with cancer whose tumors harbor *TSC1* somatic mutations. *Furthermore, interesting data was recently reported from an autopsy case study from a patient with metastatic breast cancer that received an alpha-isoform PI3K blocking agent and succumbed to her disease after a lasting clinical response (Juric et al. 2015). Extensive metastatic sampling was performed post-mortem, with the main finding being the emergence of molecular aberrations leading to loss of PTEN; thus, indicating a new mechanism of secondary resistance to PI3K blockade.* Similar approaches could be of great value when analyzing responses to agents targeting the PI3K/AKT/mTOR pathway, especially in the neoadjuvant setting.

SECTION 4.1.2: Exclusion Criteria

Patients who meet any of the following criteria will be excluded from study entry:

- History of prior or currently active small or large intestine inflammation (such as Crohn's disease or ulcerative colitis). *Any patient with a baseline medical condition involving the gastrointestinal (GI) tract or who may have a predisposition for GI toxicity requires prior approval from the Medical Monitor.*

SECTION 4.5.10: Laboratory Assessments

The following assessments will be performed at the local laboratory. The frequency of assessments is provided in Appendix 1.

- Hematology (complete blood count, including red blood cell [RBC] count, hemoglobin, hematocrit, white blood cell [WBC] count with differential [neutrophils, eosinophils, basophils, lymphocytes, monocytes, and other cells, *if applicable*]), and platelet count.

The following assessments will be performed at a central laboratory. Instruction manuals outlining sampling procedures, storage conditions, and shipment instructions and supply kits will be provided for all central laboratory assessments:

- Tumor tissue should be *from the primary tumor (not lymph nodes)* and of good quality based on total and viable tumor content. Evaluation of the patient's tumor sample for adequate tumor tissue content by a central laboratory must occur prior to initiation of study treatment. A minimum of ten unstained slides from a prior diagnostic FFPE core biopsy would be required for enrollment eligibility purposes.

A formalin-fixed, paraffin-embedded tumor block from surgical resection (Weeks 17–18) is required. If a tumor block cannot be obtained for various reasons (e.g., the tumor tissue is not sufficient at surgical resection), the site should discuss with the central study team. In such cases, paraffin-embedded, unstained slides (a minimum of 20 and up to 40 unstained slides) from a

surgical specimen are required at surgery (Weeks 17–18). *Except in the case of pCR, every effort should be made to obtain a fresh-frozen tumor tissue sample at surgery.*

SECTION 4.5.11.1: Mutational Analysis for *PIK3CA*

Somatic mutations in the *PIK3CA* gene are found in approximately 35%–40% of ER-positive breast cancers and occur most commonly in Exons 9 and 20 (*helical and kinase domain, respectively*) in the codons encoding amino acids E542, E545, and H1047 (Saal et al. 2005)....

SECTION 5.1.1.3: Management of Rash

Rash and other dermatological events should be closely monitored, and patients with severe rash should be monitored for associated signs and symptoms such as fever and hypotension that may be suggestive of a systemic hypersensitivity reaction. For severe rash, dosing of GDC-0032/*placebo* should be interrupted, and patients should be treated with supportive therapy per standard of care. Use of antihistamines, as well as topical or systemic corticosteroids, may be considered (see Table 4).

SECTION 5.1.1.4.1: Management of Diarrhea and Colitis

Patients should be closely monitored for gastrointestinal symptoms (e.g., nausea, vomiting, diarrhea, abdominal pain, stomatitis, and changes in stool, including checking for blood in stool if clinically indicated). Patients should be advised to inform the investigator if any diarrhea occurs, even if it is mild. *Weekly patient contact (e.g., telephone call) for all events of diarrhea Grades ≥ 1 is recommended to closely follow until resolution of symptoms.* Gastrointestinal symptoms should be managed per protocol guidelines and institutional standard of care. For example, prompt management of diarrhea with antidiarrheal medications should be implemented. Because of the approximately 40-hour half-life of GDC-0032, investigators should hold GDC-0032/*placebo* for Grade ≥ 2 diarrhea.

Perforated duodenal ulcer has been observed in 2 patients (one patient at 6 mg *capsule* in combination with letrozole; another patient at 6 mg *capsule* in combination with fulvestrant). Appropriate caution should be taken with the administration of medications such as aspirin, nonsteroidal anti-inflammatory drugs, and corticosteroids that can increase the risk of gastritis, peptic ulcers, or gastrointestinal perforation.

SECTION 5.2.3: ~~Non-Serious~~ Adverse Events of Special Interest (Immediately Reportable to ABCSG)

~~Non-serious~~ Adverse events of special interest are required to be reported by the investigator to ABCSG safety department immediately (i.e., no more than 24 hours after learning of the event; see Section 5.4.2 for reporting instructions). Adverse events of special interest for this study include the following:

- Grade ≥ 3 –2 diarrhea

- *Grade ≥ 1 diarrhea for > 2 weeks after following medical management guidelines in Section 5.1.1.4*

SECTION 5.4.1: Emergency Medical Contacts

Genentech's Medical Monitor Contact Information:

Medical Monitor: [REDACTED], M.D., Ph.D.

Telephone No. [REDACTED]

SECTION 5.5.1: Investigator Follow-Up

The investigator should follow each adverse event until the event has resolved to baseline grade or better, the event is assessed as stable by the investigator, the patient is lost to follow up, or the patient withdraws consent. Every effort should be made to follow all serious adverse events considered to be related to study drug or trial-related procedures until a final outcome can be reported. *With regard to the adverse event of special interest of diarrhea, it is recommended that investigators follow every adverse event of \geq Grade 1 diarrhea with weekly patient contacts (e.g., telephone calls) and follow up until resolution. Cases that do not resolve within 1–2 weeks should be aggressively managed per protocol recommendations for gastrointestinal toxicities.*

SECTION 5.6: POST-STUDY ADVERSE EVENTS

The investigator should report these events ~~by completing and faxing a paper Serious Adverse Event Reporting Form and fax cover sheet to Safety Risk Management using the fax numbers provided to investigators~~ *directly to the Sponsor or its designee, either by faxing or by scanning and emailing the Serious Adverse Event/Adverse Event of Special Interest Reporting Form using the fax number or email address provided to investigators. (see "Protocol Administrative and Contact Information & List of Investigators").*

SECTION 6.1: DETERMINATION OF SAMPLE SIZE

To control an overall, two-sided, family-wise error rate under 20% *for each analysis population*, we use a two-sided significance level of 16% and 4% for the co-primary endpoints MRI ORR, and pCR, respectively.

SECTION 6.4.1: Primary Efficacy Endpoint

...The pCR rate will also be calculated and compared at a two-sided alpha of 4% based on the same analytical approach as ORR. The two alpha values account for a family-wise type I error rate of 20% *for each analysis population*. Patients with early study termination and hence missing efficacy outcome will be considered as non-responders.

TABLE 2: Dose Modification and Management Guidelines for Hyperglycemia (Based on Fasting Blood Glucose)

Table 2 has been updated to include placebo throughout: GDC-0032/*placebo*.

TABLE 3: Dose Modification and Management Guidelines for Pneumonitis

Table 3 has been updated to include placebo throughout: GDC-0032/*placebo*.

TABLE 4: GDC-0032 Dose Modification and Management Guidelines for Rash

Table 4 has been updated to include placebo throughout: GDC-0032/*placebo*.

TABLE 5: GDC-0032 Dose Modification and Management Guidelines for Diarrhea and Colitis

Table 5 has been updated to include placebo throughout: GDC-0032/*placebo*. The following was also added to the table: *For any grade of diarrhea (≥ 1), contact patient at least weekly to monitor until resolution of symptoms. If symptoms persist beyond 2 weeks despite antidiarrheal treatment (e.g., loperamide), escalate to Grade 2 management.*

TABLE 6: GDC-0032 Dose Delay and Modification Guidelines for Stomatitis and Oral Mucositis

Table 6 has been updated to include placebo throughout: GDC-0032/*placebo*.

TABLE 7: GDC-0032 Dose Delay and Modification Guidelines for Other Clinically Significant Adverse Events

Table 7 has been updated to include placebo throughout: GDC-0032/*placebo*.

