The secondary efficacy outcome measures for this study are as follows:

- Tumor ORR, assessed by centrally assessed breast MRI via modified RECIST (Appendix 3) in *PIK3CA* WT patients
- pCR rate in breast and axilla (total pCR) by local evaluation in *PIK3CA* WT patients

The following secondary outcome measures will be performed in all enrolled patients and separated by *PIK3CA* mutation status:

- Compare letrozole plus GDC-0032 with letrozole plus placebo in terms of ORR, as measured by modified RECIST criteria (Appendix 3) using the following methods:
 - Breast ultrasound
 - Clinical breast exam (i.e., palpation)
 - Mammography
- Central assessment of changes in Ki67 levels upon treatment with letrozole plus GDC-0032 versus letrozole plus placebo from baseline to Week 3; baseline to surgery; and Week 3 to surgery
- Compare the centrally derived PEPI score upon treatment with letrozole plus GDC-0032 with letrozole plus placebo
- Evaluate the changes in enhancing tumor volume from baseline to surgery as measured by breast MRI
- Evaluate different definitions of pCR including the following: a) ypT0, ypN0, and b) yoT0/is, ypNX (breast pCR)

Safety Outcome Measures

The safety and tolerability of GDC-0032 will be assessed using the following primary safety outcome measures:

- Incidence, nature, and severity of adverse events graded according to National Cancer Institute Common Terminology Criteria for Adverse Events, version 4.0 (NCI CTCAE, v4.0)
- Incidence and type of adverse events leading to dose discontinuation, modification, or delay
- Serious adverse events
- Protocol-defined adverse events of special interest
- Clinically significant changes in vital signs and in clinical laboratory results during the adverse event reporting period (see Section 5.3.1)

Patient-Reported Outcome Measures

The PRO outcome measures for this study are as follows:

- HRQoL, including side-effects of therapy (e.g., sore mouth/tongue, difficulty swallowing, diarrhea, skin problems), and patient functioning as measured using the European Organisation for Research and Treatment of Cancer Quality of Life Questionnaire Core 30 (EORTC QLQ-C30) and the modified breast cancer module QLQ-BR23

Exploratory Outcome Measures

The exploratory outcome measures for this study are as follows:

- ORR, pCR rate, and PEPI scores according to the decrease in Ki67 after 2 weeks of letrozole plus GDC-0032 and letrozole plus placebo.

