5.2.3 Adverse Events of Special Interest (Immediately Reportable to ABCSG)

Adverse events of special interest are required to be reported by the investigator to ABCSG safety department immediately (i.e., no more than 24 hours after learning of the event; see Section 5.4.2 for reporting instructions). Adverse events of special interest for this study include the following:

- Grade 4 hyperglycemia
- Grade ≥ 3 symptomatic hyperglycemia
- Grade ≥ 2 colitis or enterocolitis
- Grade ≥ 2 diarrhea
- *Grade ≥ 1 diarrhea for >2 weeks after following medical management guidelines in Section 5.1.1.4*
- Grade ≥ 3 rash
- Grade ≥ 2 pneumonitis
- Cases of potential drug-induced liver injury that include an elevated ALT or AST in combination with either an elevated bilirubin or clinical jaundice, as defined by Hy's law (see Section 5.3.5.5)
- Suspected transmission of an infectious agent by the study drug

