5.5 FOLLOW-UP OF PATIENTS AFTER ADVERSE EVENTS

5.5.1 Investigator Follow-Up

The investigator should follow each adverse event until the event has resolved to baseline grade or better, the event is assessed as stable by the investigator, the patient is lost to follow up, or the patient withdraws consent. Every effort should be made to follow all serious adverse events considered to be related to study drug or trial-related procedures until a final outcome can be reported. *With regard to the adverse event of special interest of diarrhea, it is recommended that investigators follow every adverse event of \geq Grade 1 diarrhea with weekly patient contacts (e.g., telephone calls) and follow up until resolution. Cases that do not resolve within 1–2 weeks should be aggressively managed per protocol recommendations for gastrointestinal toxicities.*

During the study period, resolution of adverse events (with dates) should be documented on the Adverse Event eCRF and in the patient's medical record to facilitate source data verification (SDV). For follow-up reports of serious adverse events and adverse events of special interest, investigators should record all follow up information immediately (i.e., within 24 hours) on the paper Serious Adverse Event reporting form and transmit to ABCSG safety department via fax. In addition the serious adverse event and adverse event of special interest follow-up information will be captured in the EDC system. If, after follow-up, return to baseline status or stabilization cannot be established, an explanation should be recorded on the Adverse Event eCRF and paper Serious Adverse Event form, if applicable.

All pregnancies reported during the study should be followed until pregnancy outcome, and they should be reported according to the instructions provided in Section 5.4.

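### Persistent Grade 1 diarrhea counts as an adverse event of special interest only after the management guidelines were followed, so under-managed Grade 1 cases fall outside the definition

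*Protocol*

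**What the plan says.** The current Section 5.2.3 lists the AESIs that the investigator must report to the safety department within 24 hours. Three lines matter here:

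- "Grade ≥ 2 diarrhea", with no condition on duration or management.
- "Grade ≥ 2 colitis or enterocolitis", also unconditional.
- Grade 1 or higher "diarrhea for > 2 weeks after following medical management guidelines in Section 5.1.1.4".

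The third line is new in Version 4, which also lowered the diarrhea threshold on the first line from Grade 3 to Grade 2. The rationale given for the Version 4 diarrhea changes is: "The above changes were prompted by the number of suboptimally managed cases of diarrhea, one of which resulted in colitis". It adds that they are meant to increase the monitoring of diarrhea.

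Section 3.4.2 names "Protocol-defined adverse events of special interest" among the primary safety outcome measures. Section 5.5.1 recommends weekly contact for every diarrhea of Grade 1 or higher until it resolves, and continues: "Cases that do not resolve within 1–2 weeks should be aggressively managed per protocol recommendations for gastrointestinal toxicities". Table 5 in Section 5.1.1.4 moves Grade 1 symptoms that last beyond 2 weeks despite antidiarrheal treatment to the Grade 2 management row.

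**The concern.** An AESI is normally defined by the event: what happened, how severe it was, how long it lasted. Every other line in Section 5.2.3 follows that pattern. The persistent-diarrhea line alone also depends on what the site did. If the condition is taken at its word, a site that did not follow the guidelines has no AESI to report for a lasting Grade 1 diarrhea, although suboptimal management was the reason given for tightening surveillance.

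Two things are at stake. One is speed: AESIs reach the safety department within 24 hours and, under Section 5.7, the sponsor evaluates them promptly against cumulative experience. Ordinary adverse events arrive through the eCRF, which Section 7.3 expects usually within 2 weeks of the visit. The other is meaning: the AESI rate is a named safety outcome, and for this component it would reflect site compliance as well as tolerability.

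Persistent Grade 1 diarrhea matters in this protocol's own terms. Table 5 raises evaluation for colitis when it persists, and Section 5.1.1.4.1 says that steroid-responsive diarrhea and colitis have been hard to tell apart.

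**Working it through.** No figure in the plan needs reproducing; the check is one of wording. Take diarrhea that has lasted more than 2 weeks and cross grade with adherence to Section 5.1.1.4, using the Section 5.2.3 lines as written.

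| Highest grade | Guidelines followed? | Grade 2 line met? | Persistent line met? | AESI? |
|---|---|---|---|---|
| 2 or higher | Yes | Yes | Yes | Yes |
| 2 or higher | No | Yes | No | Yes |
| 1 | Yes | No | Yes | Yes |
| 1 | No | No | No | **No** |

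The persistent line changes the outcome only in the two Grade 1 rows, and it captures one of them. The row that escapes becomes reportable within 24 hours only if the event is serious (Section 5.4), or later reaches Grade 2 diarrhea or Grade 2 colitis.

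The clock is the second gap. Let *d* be the number of days from onset to the start of guideline management.

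- If the 2 weeks run from onset, the trigger is passed at 14 days.
- If they run from the start of management, it is passed at 14 + *d* days after onset.

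For illustration only, *d* = 14 gives 14 + 14 = 28 days, against a maximum GDC-0032 treatment period of 16 × 7 = 112 days; 28/112 = 25% of that period. If management never starts, the second reading never triggers. The text supports either reading.

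The line also does not say which departures from Section 5.1.1.4 count as not following it. For Grade 1, Table 5 includes institutional care with antidiarrheals, infectious work-up in some cases, and at least weekly contact. Two sites could classify the same patient differently.

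**The case against.** The strongest defence is that the line was meant to pick out diarrhea that is refractory to management, as the reporting counterpart of the 2-week step in Table 5. That is a coherent choice of signal. It does not close the gap, because refractory still presupposes that management took place. The condition makes sense as a step in a treatment table, but less so as a case definition for surveillance.

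Several stronger readings are tempting, and the documents do not support them:

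- *All diarrhea beyond 2 weeks depends on adherence.* It does not. Grade 2 and above is an AESI whatever the site did.
- *The cases that prompted the amendment would themselves escape.* The rationale gives no grade, duration or count. Any that reached Grade 2 diarrhea or Grade 2 colitis are AESIs, and any that were serious are reportable within 24 hours.
- *The events are lost.* They are not. Sections 5.3 and 5.3.1 require all adverse events to be recorded, Section 5.5.1 asks for resolution dates, and adverse event incidence by grade is a separate safety outcome. Duration over 14 days could be derived later. Weekly contacts are recommended, and adverse event contacts at Weeks 7 and 11 are scheduled.
- *Section 5.5.1 contradicts Section 5.2.3.* Its 1–2 week statement is a follow-up rule, not a reporting definition. It shows that the protocol elsewhere counts non-resolution without an adherence condition, and no more than that.
- *The undercount can be sized, or falls mainly in the GDC-0032 arm.* The 67% related diarrhea in the letrozole cohort (Section 1.7.1) is for any grade, includes 11% at Grade 3–4, and comes from 6 or 9 mg capsules taken daily, not this trial's 4 mg intermittent tablet schedule. The protocol gives no rate of persistence, no rate of non-adherence and no placebo rate.

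What stands of the objection is that the loss is confined to expedited reporting and the AESI classification.

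**Conclusion.** The point holds in a narrow form. As worded, Section 5.2.3 excludes persistent Grade 1 diarrhea that was not managed per Section 5.1.1.4, and it leaves the start of the 2 weeks undefined. That is one of four combinations of grade and adherence; the number of patients is unknown and cannot be derived from the protocol. The consequence is a missed 24-hour AESI report and a missed count in the AESI outcome, not a missing adverse event record.

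The conclusion rests on reading the line literally and on taking it to be one of the Version 4 diarrhea changes that the rationale explains, which its date and subject suggest. On that basis the wording works against the amendment's stated aim. This is an inexpensive improvement to a safety definition. It has no bearing on the efficacy analysis.

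**What to change.** Reconcile Section 5.2.3 with the aim stated for Version 4. Define the trigger as diarrhea of Grade 1 or higher lasting more than 14 days from onset, irrespective of whether the Section 5.1.1.4 guidelines were followed. Add one field to the AESI form recording whether they were followed, so that refractory and under-managed cases can be separated in the analysis. If the sponsor does want adherence as a condition, the section should say so, say what counts as adherence, and say when the 2 weeks begin.

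This alters the reporting definition only; Table 5 and the management of diarrhea stay as they are. The cost is one line of protocol text, one form field, and a few more Grade 1 AESI reports for sites and the safety department.
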